7.2 Analysis methods

7.2.1 Primary analysis

In the primary analysis, all patients will be analyzed using the FAS set.

Proportions of patients achieving clinical, IBDQ and biochemical response and remission at W8 and W16 will be calculated and reported with the associated 95% Wilson confidence interval.

The course of continuous secondary outcomes (PMS, IBDQ score, PROs and fCAL) and of the exploratory additional PMS subscore outcomes over time will be depicted by box plots showing medians, quartiles, and outlying values. For these outcomes and for Medians and associated quartiles at baseline, W8, and W16 will be reported in a table.

For these outcomes, the change from baseline will be calculated at each time point as the observed value minus the value measured at baseline. The course of change over time, will be depicted by box plots showing medians, quartiles, and outlying values. Medians and associated quartiles at W8 and W16 will be reported in a table.

The course of fCAL over time will be shown separately for patients with and without clinical response as well as for patients with and without remission at W8 and W16. Medians and associated quartiles at W8 and W16 will be reported in a table.

Correlation between PRO outcomes and PMS, PMS subscores, IBDQ score and fCAL concentrations will be assessed at BL, W8 and W16 by the Spearman correlation coefficient. For each time point the correlation coefficient will be presented in a table.

Average daily dose of Tofacitinib during the trial, active UC and others additional outcomes assessed via ultrasound, number of comorbidities and EIM number, improvement, and new occurrence will be described at W8 and 16 in descriptive tables. Categorical variables will be summarized as number and proportion, continuous variables as median with quartiles range or mean with standard deviation, as appropriate.

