3. RESEARCH QUESTIONS, OBJECTIVES AND ENDPOINTS

Table 3. Study Objectives and Endpoints

Primary Objective:	Primary Endpoint:
Evaluate the RW effectiveness of tofacitinib induction therapy in patients with UC.	Proportion of participants achieving clinical response ^a at W8.
Secondary Objectives:	Secondary Endpoints:
Evaluate RW response to tofacitinib treatment based on PMS.	
Proportion of participants achieving clinical remission^b at W8.Proportion of participants achieving clinical response^a at W16.Proportion of participants achieving clinical remission^b at W16.
Evaluate the RW response to tofacitinib treatment on quality of life based on IBDQ score.	
Proportion of participants achieving IBDQ remission^c at W8.Proportion of participants achieving IBDQ remission^c at W16.Proportion of participants achieving IBDQ response^d at W8.Proportion of participants achieving IBDQ response^d at W16.
Evaluate RW response to tofacitinib treatment based on fCAL concentrations.	
Proportion of participants achieving biochemical remission^e at W8.Proportion of participants achieving biochemical remission^e at W16.
Elucidate fCAL and PRO responses to tofacitinib induction therapy for UC.	Median changes from baseline in PROs and fCAL over time (ie, map response curves).
Assess whether PRO responses occur prior to, with or lag behind clinical responses.	Correlations between changes in amplitude and timing of PMS, PROs, IBDQ score and fCAL concentrations.
Verify the validity of fCAL as a convenient surrogate biomarker to assess early response to tofacitinib treatment.	
Median fCAL concentrations over time stratified by W8 and W16 clinical remission status.^bMedian fCAL concentrations over time stratified by W8 and W16 clinical response status.^aMedian fCAL concentrations at W8 by W8 clinical response status.^a
Exploratory Objectives:	Exploratory Endpoints:
Assess effect of prior exposure to biologics, concomitant medications and tofacitinib induction dose, on treatment outcomes.	Stratification of PMS outcomes, PROs and fCAL levels based on: i) prior exposure to TNFi, vedolizumab and ustekinumab; ii) concomitant medication with corticosteroids or aminosalicylic acids; iii) predominant tofacitinib dose.

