9. STATISTICAL CONSIDERATIONS

9.1. Statistical Hypotheses

The study hypotheses that will be subject to statistical testing are that:

- Tofacitinib induction therapy is associated with a rapid improvement in the PMS, intestinal inflammation (ie, reduced fCAL concentrations), QoL and symptoms (PROs).
- Changes in different types of treatment outcomes (ie, PMS, PROs and fCAL concentrations) are correlated.
- Improvements in PROs and fCAL concentrations can predict treatment outcomes (clinical outcome measures) at end of induction therapy.

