9.5.2. Primary Analysis

Proportions of participants achieving clinical, IBDQ and biochemical response* and remission† at Week 8 and Week 16 will be calculated and reported with the associated 95% Wilson confidence interval.

The course of continuous secondary outcomes (PROs and fCAL) over time will be depicted by box plots showing medians, quartiles, and outlying values.

* Clinical response: (1) Reduction in PMS from baseline of >2 points or (2) achieving clinical remission.¹²

IBDQ response: IBDQ score ≥ 16 points higher than IBDQ baseline score.

† Clinical remission: PMS of ≤ 2 with no subscore > 1 .¹²

IBDQ remission: IBDQ score ≥ 170 .¹²

Biochemical remission: fCAL concentration ≤ 250 mg/g.¹¹

Correlation between PMS, PROs, IBDQ score and fCAL concentrations will be assessed by the Spearman correlation coefficient.

The course of fCAL over time will be shown separately for participants with and without clinical response, as well as for participants with and without remission at Week 8 and Week 16.

These analyses will also be conducted on the subset of participants that complete 8 weeks of tofacitinib therapy.

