2.2 Objectives

This study aims to generate granular real-world data on tofacitinib therapy in UC and enable a characterization of the relationship between changes in PMS, PROs and intestinal inflammation during tofacitinib induction therapy.

CTU Bern	SAP for: Study A3921395 KIC-START	Version: 1.0
CTU Bern	Template: Statistical Analysis Plan (SAP) Code: CS_STA_TEM-11	Version: 03 Valid from: 28.02.2019 Page 7 of 44

3. Study methods

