8.2.3 Temporal variation of PMS, PROs and fCAL concentration

Value and change from baseline at baseline, W8 and W16 of PMS, PROs (each component separately) and fCAL concentration (values presented as median and quartiles).

Category	Name	Value at				Change from baseline at	
		Baseline	W8	W16	W8	W16	
PRO	Stool frequency	Median [Q1;Q3]	Median [Q1;Q3]	Median [Q1;Q3]	Median [Q1;Q3]	Median [Q1;Q3]	
PRO	Rectal bleeding						
PRO	Urgency of defecation						
PRO	Abdominal pain						
PRO	Quality of sleep						
PRO	Daily fatigue						
PRO	Weekly fatigue						
PRO	Quality of life (IBDQ)						
PMS	PMS						
fCAL	fCAL concentration						

8.2.3.1 Temporal variation of the fcal concentration in patients with and without clinical response and remission

Value and change from baseline at baseline, W8 and W16 of fCAL concentration stratified by clinical outcomes at W8 and W16. (Values presented as median and quartiles)

Outcome	Value at				Change from baseline at	
	Baseline	W8	W16	W8	W16	
fCAL all patients						
fCAL for patients with clinical response at W8						
fCAL for patients without clinical response W8						
fCAL for patients with clinical response at W16						

CTU Bern	SAP for: Study A3921395 KIC-START	Version: 1.0
----------	-----------------------------------	--------------

CTU Bern	Template: Statistical Analysis Plan (SAP)	Version: 03
	Code: CS_STA_TEM-11	Valid from: 28.02.2019

u^b
UNIVERSITÄT
BERNFaculty of Medicine
CTU Bern

fCAL for patients without clinical response W16

fCAL for patients with clinical remission at W8

fCAL for patients without clinical remission W8

fCAL for patients with clinical remission at W16

fCAL for patients without clinical remission W16

Footnote: Definitions for clinical response and clinical remission according to IUS assessment.

CTU Bern	SAP for: Study A3921395 KIC-START	Version: 1.0
CTU Bern	Template: Statistical Analysis Plan (SAP) Code: CS_STA_TEM-11	Version: 03 Valid from: 28.02.2019 Page 39 of 44

8.3 Correlation between PRO and PMS, IBDQ score and fCAL concentrations outcomes.

Correlations measures (Spearman correlation coefficients) will be assessed at BL (Table a), W8 (Table b) and W16 (Table c). Results will be presented in similar but separated tables.

	Stool frequency	Rectal bleeding	Urgency of defecation	Abdominal pain	Quality of sleep	Daily fatigue	Weekly fatigue	Quality of life (IBDQ)	PMS	PM S sub-score1	PM S sub-score2	PM S sub-score3	fCAL
Stool frequency													
Rectal bleeding													

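### The secondary endpoint is correlation of changes, but SAP 7.2.1 and 8.3 plan only Spearman correlations of score levels at each visit, and SAP section 9 does not record this

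*SAP*

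**What the plan says.** Three places put the target on changes.

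- Protocol section 3, Table 3, gives the secondary endpoint as "Correlations between changes in amplitude and timing of PMS, PROs, IBDQ score and fCAL concentrations". It serves the objective of finding out whether PRO responses come before, with or after clinical response.
- Protocol 9.1 hypothesises: "Changes in different types of treatment outcomes (ie, PMS, PROs and fCAL concentrations) are correlated".
- SAP 2.2 repeats the aim: "enable a characterization of the relationship between changes in PMS, PROs and intestinal inflammation during tofacitinib induction therapy".

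The analysis text is about something else.

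- Protocol 9.5.2 says "Correlation between PMS, PROs, IBDQ score and fCAL concentrations will be assessed by the Spearman correlation coefficient", with no reference to change or timing.
- SAP 7.2.1 fixes the visits: "IBDQ score and fCAL concentrations will be assessed at BL, W8 and W16 by the Spearman correlation coefficient".
- SAP 8.3 confirms the layout: "Correlations measures (Spearman correlation coefficients) will be assessed at BL (Table a), W8 (Table b) and W16 (Table c"), with the scores themselves as rows and columns.

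SAP 7.2.1 does derive change scores: "the change from baseline will be calculated at each time point as the observed value minus the value measured at baseline". It uses them only for box plots and for medians with quartiles. SAP 8.2.3.1 tabulates "Value and change from baseline at baseline, W8 and W16 of fCAL concentration stratified by clinical outcomes at W8 and W16". SAP 7.2.2 at most repeats the same analyses in the on-tofacitinib set, and 7.2.3 to 7.2.5 are marked not applicable. SAP section 9 lists the sample size, the added exploratory outcomes, the dropped per-protocol set, and the dropped baseline-effect and subgroup analyses. It has no entry on this endpoint.

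**The concern.** If the SAP is followed as written, a stated secondary endpoint goes unestimated and nobody is told. Two measures can correlate across patients at Week 8 because some patients are generally worse on both, whether or not the two improve together. A reader who knows the protocol's hypothesis could take a Week 8 level correlation as evidence that symptoms, PMS and fCAL improve in parallel, which the planned tables cannot show.

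The timing half of the endpoint has a second gap. Under protocol 8.1.1.1 and the schedule in 1.3, PMS is scheduled only at baseline, W8 and W16 (plus early termination). PRO response therefore cannot be ordered against PMS-defined response within the first 8 weeks. Neither document says so.

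**Working it through.** **1. Are the planned correlations levels or changes?** SAP 8.3 has one matrix for baseline, one for W8 and one for W16. Change from baseline is zero for every patient at baseline, so a baseline matrix of changes would have no defined coefficients. The matrices must hold levels.

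**2. Does anything else relate changes to each other?** SAP 8.2.3.1 shows fCAL change by clinical response and remission status. Both are PMS-based, so this partly covers the PMS-fCAL pair, with PMS reduced to yes or no. No PRO or IBDQ change is related to any other change.

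**3. How many pairs?** Counting IBDQ once, as its own measure, SAP 7.2.1 names 7 PROs (stool frequency, rectal bleeding, urgency, abdominal pain, sleep, daily fatigue, weekly fatigue) against 6 measures (PMS, three PMS subscores, IBDQ, fCAL): 7 × 6 = 42 pairs per visit. None is planned on change.

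**4. Do level correlations determine change correlations?** The plan gives no figure to reproduce, so this is an illustration with assumed inputs. For two measures with equal variances at both visits, let r_BL and r_W8 be the same-visit correlations, a and b the correlation of each measure with itself across visits, and c1 and c2 the correlations of one measure at one visit with the other measure at the other visit. Then

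r_change = (r_BL + r_W8 − c1 − c2) / (2·√((1 − a)(1 − b))).

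With r_BL = r_W8 = r, a = b and c1 = c2 = c this becomes (r − c)/(1 − a). It equals r exactly when c = a × r.

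Take r = a = 0.5. Then r_change = (0.5 − c)/0.5 = 1 − 2c. The Spearman columns come from 400,000 simulated normal draws.

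| c | r_change = 1 − 2c | Level Spearman (both visits) | Change Spearman |
|---|---|---|---|
| 0.10 | 0.8 | 0.48 | 0.79 |
| 0.25 | 0.5 | 0.48 | 0.48 |
| 0.50 | 0.0 | 0.48 | 0.00 |

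The smallest eigenvalues of the three correlation matrices are 0.10, 0.25 and 0.50, so all three are valid. The matrix stays positive semidefinite for c from 0 to 1, so r_change can run from 1 to −1. The two quantities also agree at a = 0.3, c = 0.15, where (0.5 − 0.15)/0.7 = 0.5, and at a = 0.7, c = 0.35, where (0.5 − 0.35)/0.3 = 0.5. The planned tables report neither a nor c.

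**5. How precise would change correlations be?** Use Fisher's z with SE = √((1 + r²/2)/(n − 3)). The n of 18 is from SAP 3.3; 15 complete pairs is an assumption.

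- n = 18, r = 0.5: z = 0.549, SE = √(1.125/15) = 0.274, 95% CI 0.01 to 0.80.
- n = 18, r = 0.3: z = 0.310, SE = √(1.045/15) = 0.264, 95% CI −0.20 to 0.68.
- n = 15, r = 0.5: SE = √(1.125/12) = 0.306, 95% CI −0.05 to 0.82.

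**The case against.** The strongest reply is that the SAP did not depart from the protocol's analysis section. Protocol 9.5.2 already names only the scores, and the SAP follows it, adding visits and PMS subscores. That is right about where the mismatch began. It does not remove the Table 3 endpoint, the 9.1 hypothesis or the aim kept in SAP 2.2. Section 9 is the natural place to settle the conflict.

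Second, the SAP plots the course of change over time for each measure, which says something about when each one moves. In addition, the App collects stool frequency and rectal bleeding on the Mayo grading daily to Week 2 and twice weekly to Week 8, and fCAL is measured four times in the first week and then weekly. PRO timing could therefore be described against those measures. This stands as an opportunity, but separate box plots do not relate one patient's changes to each other, and PMS-defined response remains unobserved between baseline and Week 8.

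Third, the illustration uses assumed inputs. The extremes of −1 and 1 sit at the edge of what is admissible, negative values need a cross-visit correlation above the same-visit one, and at c = a × r there is no gap. All true: the illustration shows that the endpoint is not identified, not that it will be badly misestimated.

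Fourth, the 8.3 shell has 13 variables, hence 13 × 12/2 = 78 pairs, and SAP 8.2.3 labels IBDQ a PRO, so other counts are possible. The counts here follow the 7.2.1 text and the 9.1 wording about different types of outcome. The core point does not depend on them.

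Last, many coefficients at n = 18 are weak evidence, and protocol 4.2 calls the second 8 weeks exploratory. The planned level coefficients share the sample-size limit, and the SAP does not give sample size as a reason for leaving change correlations out.

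**Conclusion.** The point holds. The endpoint, the hypothesis and the SAP's own aim concern changes; the planned correlations concern levels; section 9 is silent. Except for the partial PMS-fCAL table, the plan estimates a different quantity from the one it set out to estimate. How far the two differ cannot be known from the documents. With equal variances and r = a = 0.5 assumed, the same level Spearman of 0.48 goes with anything from 0.00 to 0.79 across three plausible-looking inputs. The primary endpoint is unaffected and the study is descriptive, so this should be corrected but does not threaten the main result.

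**What to change.** 1. In SAP 7.2.1 and 8.3, add Spearman correlations of change from baseline at W8 and at W16 as the analysis of this endpoint. Use the 42 pairs named in 7.2.1 plus PMS-fCAL, PMS-IBDQ and IBDQ-fCAL: 42 + 3 = 45 per visit. Report each with n and a 95% CI, labelled descriptive. Keep the level tables as supportive.
2. In SAP section 9, reconcile protocol Table 3, protocol 9.5.2 and the SAP. State there that scheduled PMS exists only at baseline, W8 and W16, so PRO timing cannot be ordered against PMS-defined response within the first 8 weeks.

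The cost is two tables (45 × 2 = 90 coefficients) from change scores that 7.2.1 already derives, and a short text; no new data. The downsides are wide intervals, as shown above, and the number of them: if all 90 true correlations were zero, about 90 × 0.05 = 4.5 intervals would still be expected to exclude zero, which is why the descriptive label matters. The assay range of 30 to 1000 µg/g (protocol 8.1.1.3) also means that fCAL values at the upper limit blunt the measured fCAL change.

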7.2.2 Secondary analyses

If more than 2 patients are excluded from the on-tofacitinib analysis set (OTAS), all analysis described in the primary analysis section above will be conducted on the OTAS population.

7.2.3 Sensitivity analyses

Not applicable.

CTU Bern	SAP for: Study A3921395 KIC-START	Version: 1.0
CTU Bern	Template: Statistical Analysis Plan (SAP) Code: CS_STA_TEM-11	Version: 03 Valid from: 28.02.2019

7.2.4 Subgroup analyses

Not applicable.

7.2.5 Additional analyses

Not applicable.

7.3 Interim analyses

Not applicable.

7.4 Missing data

Missing data will be ignored.

Rules for calculations of the different scores in the presence of missing information are detailed in the above sections.

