IBDQ score	Continuous (score varying between from 32 to 224)	
Variables: <code>pro_ibdq_x</code> (with X varying from 1 to 32)
 
Derivation: at each reported time point. For each variable, 7 answers are possible. Answers are ranked from the 'worst' to 'best' quality of life, and replaced by a score varying from 1(worst) to 7(best). Scores obtained for each of the 32 variables are then summed up. If any of the <code>pro_ibdq_x</code> (with X varying from 1 to 32) variables is missing the score is coded as missing.

Weekly fatigue score (FACT-F score)	Continuous (score varying between from 0 to 52)	
Variables <code>pro_facit_an1, pro_facit_an2, pro_facit_an3, pro_facit_an4, pro_facit_an5, pro_facit_an7, pro_facit_an8, pro_facit_an12, pro_facit_an14, pro_facit_an15, pro_facit_an16, pro_facit_hi12, pro_facit_hi7</code>
 
Derivation: at each reported time point. For each variable, 5 answers are possible. Answers are converted to score (see below), scores obtained for each of the 13 listed variables are then summed up. If any of the variables use to derive the score is missing the score is coded as missing.

CTU Bern	SAP for: Study A3921395 KIC-START	Version: 1.0

CTU Bern	Template: Statistical Analysis Plan (SAP)	Version: 03	Page 12 of 44
	Code: CS_STA_TEM-11	Valid from: 28.02.2019	

Variable definition	Variable type	Derivation
		Scoring system: Not at all =0; A little bit =1; Somewhat =2; Quite a bit =3; Very much =4
PMS score	Continuous	Variables: pms_stool_freq, pms_rect_bleed, pms_glob_ass Derivation: At each reported time point. For each variable, 4 answers are possible. Answers are converted to score from 0 (normal) to 3 (more severe condition), scores obtained for each of the 3 listed variables are then summed up. If any of the variables used to derive the score is missing the score is coded as missing.
PMS stool frequency subscore	Continuous	Variable: pms_stool_freq Derivation: At each reported time point. 4 answers are possible. Answers are converted to score from 0 (normal) to 3 (more severe condition).
PMS rectal bleeding subscore	Continuous	Variable: pms_rect_bleed Derivation: At each reported time point. 4 answers are possible. Answers are converted to score from 0 (normal) to 3 (more severe condition).

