5.2 Analysis populations

5.2.1 Full analysis set (FAS)

The full analysis set (FAS), will include all participants who were included in the study (i.e., performed baseline visit and received a study identification number). This analysis will therefore include all study participants, regardless of their adherence to study protocol procedures.

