6.7 Withdrawal/follow-up

Number and percentage of withdrawal and lost to follow-up will be presented in the flow chart (see section 6.3).

CTU Bern	SAP for: Study A3921395 KIC-START	Version: 1.0
----------	-----------------------------------	--------------

CTU Bern	Template: Statistical Analysis Plan (SAP)	Version: 03	Page 24 of 44
	Code: CS_STA_TEM-11	Valid from: 28.02.2019	

u^b^b
UNIVERSITÄT
BERNFaculty of Medicine
CTU Bern

7. Analysis

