7.1 Outcome definitions

Table 7-a: Derivation of study outcomes

Outcome	Definition	eCRF sheet	Variable	Variable type	Derivation	Outcome type
PRIMARY OUTCOME						
Clinical response at W8	(1) reduction in PMS from baseline of ≥ 2 points or (2) achieving clinical remission	PMS	PMS score (see section 4.3) pms_stool_freq pms_rect_bleed pms_glob_ass	continuous	Yes: If (PMS at W8- PMS at baseline ≥ 2) OR PMS at W8 ≤ 2 AND pms_stool_freq<2 AND pms_rect_bleed<2 AND pms_glob_ass<2 at W8.	Binary: Yes, no
SECONDARY OUTCOMES						
Clinical response at W16	(1) reduction in PMS from baseline of ≥ 2 points or (2) achieving clinical remission		PMS score (see section 4.3) pms_stool_freq pms_rect_bleed pms_glob_ass	continuous	Yes: If (PMS at W16- PMS at baseline ≥ 2) OR PMS at W16 ≤ 2 AND pms_stool_freq<2 AND pms_rect_bleed<2 AND pms_glob_ass<2 at W16.	Binary: Yes, no
Clinical remission W8/W16	Clinical remission: PMS of ≤ 2 with no subscore >1		PMS score (see section 4.3) pms_stool_freq pms_rect_bleed pms_glob_ass	continuous	Yes: PMS at W8 (or 16) ≤ 2 AND pms_stool_freq<2 AND pms_rect_bleed<2 AND pms_glob_ass<2 at W8 (or 16).	Binary: Yes, no
CTU Bern	SAP for: Study A3921395 KIC-START		Version: 1.0			

CTU Bern	Template: Statistical Analysis Plan (SAP)	Version: 03
	Code: CS_STA_TEM-11	Valid from: 28.02.2019

u^b^b
UNIVERSITÄT
BERN

Outcome	Definition	eCRF sheet	Variable	Variable type	Derivation	Outcome type
IBDQ remission at W8/W16	IBDQ remission: IBDQ score ≥ 170		IBDQ score calculated as described in section 4.3 at W8 and 16	continuous	Yes: IBDQ at W8 (or 16) ≥ 170	Binary: Yes, no
IBDQ response at W8/W16	IBDQ response: IBDQ score ≥ 16 points higher than IBDQ baseline score		IBDQ score calculated as described in section 4.3 at baseline, W8 and 16	continuous	Yes: IBDQ at W8 (or 16) – IBDQ at BL ≥ 16	Binary: Yes, no
Biochemical remission at W8/W16	Biochemical remission: fCAL concentration $\leq 250 \mu\text{g/g}$		fcal_value	continuous	Yes: fcal_value $\leq 250 \mu\text{g/g}$	Binary: Yes, no
PROs						
Stool frequency		Stool freq, rect. bleed, NRS	pro_stool_freq	Score (0-3), continuous		Continuous
Rectal bleeding			pro_rect_bleed	Score (0-3), continuous		Continuous
Urgency of defecation			pro_nrs_urgency	Continuous		Continuous
Abdominal pain			pro_nrs_abd_pain	Continuous		Continuous
Quality of sleep			pro_nrs_qual_sleep	Continuous		Continuous
Daily fatigue			pro_nrs_fatigue	Continuous		Continuous

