8.2.2 Efficacy Outcomes at W8 and W16

Legend:

	Primary outcome
	Secondary outcomes
	Exploratory outcomes

a. Main outcomes

Outcome	Proportion (%) of outcomes (n/N) [95% CI] *	
	W8	W16
Clinical response	% (n/N) [CI]	% (n/N) [CI]
Clinical remission	% (n/N) [CI]	% (n/N) [CI]
IBDQ response	% (n/N) [CI]	% (n/N) [CI]
IBDQ remission	% (n/N) [CI]	% (n/N) [CI]
Biochemical remission	% (n/N) [CI]	% (n/N) [CI]
FMS response	% (n/N) [CI]	% (n/N) [CI]
Remission	% (n/N) [CI]	% (n/N) [CI]
Mucosal healing	% (n/N) [CI]	% (n/N) [CI]
Response according to IUS assessment	% (n/N) [CI]	% (n/N) [CI]
Remission according to IUS assessment	% (n/N) [CI]	% (n/N) [CI]
Individual improvement in EIM	% (n/N) [CI]	% (n/N) [CI]
Categorical improvement in EIM	% (n/N) [CI]	% (n/N) [CI]

Footnotes:

CTU Bern	SAP for: Study A3921395 KIC-START	Version: 1.0
----------	-----------------------------------	--------------

CTU Bern	Template: Statistical Analysis Plan (SAP)	Version: 03
	Code: CS_STA_TEM-11	Valid from: 28.02.2019

* 95% Wilson confidence interval

Definitions for clinical response, clinical remission, IBDQ response, IBDQ remission, Biochemical remission, FMS response, remission, mucosal healing, response according to IUS assessment, remission according to IUS assessment, improvement in EIM.

**Results presented for each EIM and EIM category

*** Result presented for ascending colon, transverse colon, descending colon and sigmoid colon.

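### As most naturally read, the SAP reports Week 8 clinical response among observed cases only, with no full-analysis-set figure or bounds beside it, although it says it analyses all FAS participants.

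*SAP*

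**What the plan says.** SAP 7.2.1: "In the primary analysis, all patients will be analyzed using the FAS set". SAP 5.2.1 defines the FAS as everyone with a baseline visit and a study number, and adds: "This analysis will therefore include all study participants, regardless of their adherence to study protocol procedures". The precision statement in SAP 3.3 uses all 18 enrolled.

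Other sections narrow this:

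- SAP 4.3, on the PMS: "If any of the variables used to derive the score is missing the score is coded as missing".
- SAP 7.4: "Missing data will be ignored". Its only other sentence refers back to the score rules.
- SAP 7.1 derives the primary outcome as "Yes: If (PMS at W8- PMS at baseline ≥ 2) OR PMS at W8 ≤ 2 AND" and so on through the three subscores. It gives the condition for a yes and no branch for a PMS that is missing. (The direction of the subtraction in that line is a separate matter.)
- SAP 8.2.2 heads the results column "Proportion (%) of outcomes (n/N) [95% CI" and does not define N.
- The entry under "7.2.3 Sensitivity analyses" is that none apply.
- SAP 6.7: "Number and percentage of withdrawal and lost to follow-up will be presented in the flow chart". Missed or incomplete PMS assessments are not mentioned there.

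**The concern.** The stated population is all 18 participants, but the missing-data rule removes anyone whose Week 8 response cannot be determined. The two agree only if nobody is missing. Otherwise the reported proportion describes those who were assessed, and the SAP plans nothing to show how far the whole set could differ.

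This proportion is the sole primary result of a small single-arm study. SAP 3.4 excludes formal hypothesis testing, so no test decision is at risk. What is at stake is the size of the estimate and whether a reader can judge it.

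**Working it through.** **Inputs.** Expected response 60%, 18 enrolled, 95% Wilson interval 37.6 to 78.9% (SAP 3.3). Assumptions: all 18 are in the FAS, and m = 1 to 4 have an undeterminable Week 8 response. The documents give no value for m.

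**Reproducing the plan's figure.** The Wilson limits are [p + z²/(2n) ± z√(p(1−p)/n + z²/(4n²))] / (1 + z²/n). With p = 0.60, n = 18 and z = 1.96, the centre is 0.7067/1.2134 = 0.5824 and the half-width is 0.2502/1.2134 = 0.2062. This gives 37.6 to 78.9%, as stated, with all 18 in the denominator. The interval is 78.9 − 37.6 = 41.3 points wide.

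**Gap at the expected rate.** Let p be the response rate among the 18 − m observed.

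- Observed case: p.
- Full FAS, missing as non-response: p(18 − m)/18, which is lower by p·m/18.
- Best case, missing as response: p + (1 − p)·m/18.

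With p = 0.60:

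| m | Observed case | Full FAS | Gap (points) | Best case |
|---|---|---|---|---|
| 0 | 60.0% | 60.0% | 0 | 60.0% |
| 1 | 60.0% | 56.7% | 3.3 | 62.2% |
| 2 | 60.0% | 53.3% | 6.7 | 64.4% |
| 3 | 60.0% | 50.0% | 10.0 | 66.7% |
| 4 | 60.0% | 46.7% | 13.3 | 68.9% |

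**Check with whole participants** (counts near 60% observed, 95% Wilson intervals):

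| m | Observed case | Full FAS | Best case |
|---|---|---|---|
| 1 | 10/17 = 58.8% (36.0–78.4) | 10/18 = 55.6% (33.7–75.4) | 11/18 = 61.1% (38.6–79.7) |
| 2 | 10/16 = 62.5% (38.6–81.5) | 10/18 = 55.6% (33.7–75.4) | 12/18 = 66.7% (43.7–83.7) |
| 3 | 9/15 = 60.0% (35.7–80.2) | 9/18 = 50.0% (29.0–71.0) | 12/18 = 66.7% (43.7–83.7) |
| 4 | 8/14 = 57.1% (32.6–78.6) | 8/18 = 44.4% (24.6–66.3) | 12/18 = 66.7% (43.7–83.7) |

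The gaps between observed case and full FAS are 3.3, 6.9, 10.0 and 12.7 points, in line with the formula.

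**Direction.** If the missing participants respond at rate q, the observed-case rate exceeds the rate over all 18 by (m/18)(p − q). This is positive only if q < p. The full-FAS row is the case q = 0 and the best case is q = 1.

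**What can be determined from an incomplete PMS.** Remission under SAP 7.1 requires every subscore to be below 2. One recorded subscore of 2 or 3 therefore settles non-remission even if another is missing. It does not settle non-response, because the 2-point reduction remains possible.

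**The case against.** The strongest reply is that the rule is largely there already. SAP 4.3 makes an incomplete PMS missing, SAP 7.4 ignores missing data, and SAP 8.2.2 prints n/N for each endpoint and visit. That points to an observed-case rate with its denominator shown, and a reader who knows 18 were enrolled can compute n/18. A reader might infer instead that the denominator is wholly open, with missing returned as a no and N = 18 being just as valid a reading. The documents do not support that: returning a no would impute an outcome, which is the opposite of ignoring missing data. SAP 7.8 also has a second statistician reproduce the primary analysis and requires any difference to be resolved. On this part the objection stands, and an explicit definition of N is a clarification.

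It is also fair that missing data may be few. Protocol 7.1 keeps participants in the study after they stop tofacitinib, Protocol 8.1.1.1 makes an unassessed PMS a deviation, and the Week 8 window is ±14 days. The shifts are smaller than the 41.3-point interval.

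This does not remove the mismatch between the stated population and the reported figure. SAP 7.8 does not supply a full-FAS result. The on-tofacitinib analysis in SAP 7.2.2 is conditional, selects on continued treatment and inherits the same missing-data rule. Replacing participants who leave before Week 8 (Protocol 7.2 and 9.2) does not take them out of the FAS. The planned flow chart would not identify a missed or incomplete PMS in someone who stayed in the study.

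**Conclusion.** The point holds as a worthwhile improvement. The SAP's most natural reading is an observed-case proportion, which does not deliver the stated analysis of all FAS participants or match precision computed on all 18. At 60% response among those observed, the gap to the full-FAS non-response figure is 3.3 to 13.3 points for an assumed 1 to 4 missing. With none missing it is zero.

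Three stronger conclusions are tempting but unsupported:

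- **That the estimate is biased upward.** This is so only if participants without an evaluable PMS respond less often, and the documents do not show it.
- **That the shift could reach about 19 points.** That needs 12 responders among 14 observed: 12/14 − 12/18 = 85.7% − 66.7% = 19.0 points. The observed rate of 85.7% lies above even the upper planned limit of 78.9%.
- **That the sponsor's early stop caused missing outcomes.** SAP 3.1, 3.3 and 9 say that recruitment stopped. They do not say that follow-up of the 18 was cut short. Protocol 7.1 only lists study termination as a possible reason for discontinuation.

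**What to change.** Before database lock:

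1. In SAP 7.4 and 8.2.2, state that N in the observed-case row is the number of participants whose response or remission can be determined. Count any recorded subscore of 2 or 3 as non-remission even if the PMS is incomplete.
2. In SAP 7.2.3, replace the present entry with a full-FAS row (N = 18, undeterminable counted as non-response) and a best-case bound. Give each a Wilson interval, for clinical response and clinical remission at Week 8 and Week 16.
3. Report the number undeterminable at each visit, with reasons.

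No analysis of the PMS collected at early termination is needed, since it is not a Week 8 measurement.

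The cost is SAP wording and a few table rows, with no new data. The drawback is that the full-FAS figure is conservative if data are missing for reasons unrelated to efficacy. The observed-case row beside it shows by how much the two differ.
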